Title: A Randomized Controlled Trial of Prevena™ Incisional Negative Pressure Wound Therapy to Reduce Surgical Site Infection in Re-operative Colorectal Surgery.

Authors: [name], [name], [name], [name], [name].

Institution: Department of Colorectal Surgery, Digestive Disease Institute, Cleveland Clinic, [name].

Introduction:

Surgical site infections (SSIs) are a common problem and a significant cause of morbidity in surgical patients. They present a substantial burden to the health care system in the United States and contribute more than 1.6 billion dollars in excess cost and 1 million in extra hospital days in affected patients¹. SSIs are associated with a multitude of complications including an increased risk of incisional hernia and prolonged hospital stay². Despite optimum surgical care there remains an inability to significantly reduce SSI rates following colorectal surgery and this field represents a critical priority for study³. When one examines the control arms of recent high quality randomized controlled trials, the SSI rate following colorectal surgery ranges from 22.0-26.1%⁴⁻⁶, emphasizing the prevalence of this complication.

Many strategies have been attempted to reduce SSI rates. The Centers for Medicare and Medicaid Services introduced the Surgical Care Improvement Project infection project with the aim of reducing SSI incidence and morbidity. These measures include prophylactic intravenous antibiotics administered within 1 hour of skin incision, appropriate prophylactic antibiotic selection, discontinuation of prophylactic antibiotics within 24 hours after surgery, appropriate hair removal, and maintenance of perioperative normothermia⁷. Despite the enforcement of these measures through quality reporting and pay-for-performance measures, significant controversy exists as to their overall effectiveness⁸, especially in the high-risk colorectal surgical population⁹. Laparoscopic surgery has been shown to improve SSI rates in the colorectal population¹⁰; however, not all patients are appropriate candidates for this approach and the inability of promising interventions such as wound edge protection⁶ and gentamicin sponges⁴ to improve SSI rates following colorectal surgery mandate the investigation of novel techniques.

Initiated in the orthopaedic literature, a new technique of wound dressing has been described to reduce SSI¹¹. Incisional negative pressure wound therapy (NPWT) using devices such as the Prevena™ involves applying a wound vacuum sponge over a standard wound closure (including fascial closure and skin closure with staples). The incisional NPWT dressing is then left in place for 5 to 7 days before removal. A recent retrospective study by Bonds *et al.* described the ability of incisional NPWT to reduce SSI rates in open colorectal surgery from 29.3-12.5%¹².

The aim of the current study is to assess the clinical effectiveness of incisional NPWT to reduce SSI rates in open, re-operative colorectal surgery. The primary endpoint of this study is the occurrence of superficial SSI within 30 days after surgery and the secondary endpoints include, length of hospital stay and cost effectiveness.

Methods

Study design and patients

This investigator-initiated trial will be a prospective, unicentre, randomized controlled trial. It is planned to be conducted from July 2015 to June 2018 at the Department of Colorectal Surgery at the Cleveland Clinic, Ohio. However, it is likely given the high volume practice of department, that

it will be completed sooner. Patients aged over 18 years undergoing re-operative colorectal surgery defined as the excision or revision of a prior anastomosis, intestinal resection with an incisional hernia repair or enterocutaneous fistula repair in both elective and emergency settings are eligible for enrolment. Patients undergoing completion proctectomy and ileal pouch anal anastomosis with a mucous fistula from their rectal stump will also be included. Laparoscopic or laparoscopic assisted procedures, patients who had undergone a laparotomy within the preceding three months and an active SSI at the time of surgery will be excluded. Institutional review board approval will be sought before trial commencement, written informed consent will be obtained from all patients before enrolment and the trial will be registered with clinicaltrials.gov. The number and reason of patients excluded and lost to follow-up will be prospectively recorded.

Randomization

Enrolled patients will be randomly assigned through a concealed centralized secure web based system in a 1:1 ratio to either the control arm (standard post-operative care) or the intervention arm (the application of the Prevena™ NPWT system (Acelity, San Antonio, TX)). Randomization will be performed when the patient attends the last preoperative visit using the REDCap™ (Research Electronic Data Capture) secure online system. In our department this visit occurs on the day prior to surgery, facilitating ease of enrolment.

The departmental SSI prevention bundle will be used in all cases including preoperative mechanical bowel preparation with the addition of oral antibiotics, a preoperative patient shower with Hibiclens (Mölnlycke Health Care, Norcross, GA), intravenous antibiotics administered 1 hour before skin incision, antiseptic preparation of the abdomen, the routine use of a wound protector, surgical glove changes following contamination and before wound closure and separate instruments used for wound closure. The non-NPWT dressing will be left in place for 48 hours before changing.

Surgeons in the Colo-rectal surgery department trained in the application of the Prevena™ NPWT system will enroll and operate on patients included in this trial. All wounds will be irrigated with sterile saline before closure and the attending staff surgeon will perform all closures themselves. The fascia will be closed with interrupted or running # 1 Maxon™ (Covidien), followed by skin closure with staples. Control patients with standard wound dressings will have gauze and tape dressings applied while those in the NPWT group will have the Prevena™ system applied; both before the maturation of the ostomy to avoid contamination of the wound with enteric content. The Prevena™ system will remain in place for 7 ± 1 days. However, if concern exists for the patients wound, it will be removed, the wound assessed and this will be recorded as a break from trial protocol. The Prevena™ will however be reapplied if the wound is not infected.

Efficacy outcomes

The primary endpoint will be the occurrence of superficial surgical site infection within 30 days after the operation. Diagnosis will be based on criteria developed by the Centers for Disease Control (CDC)¹³. All wound assessors will be experienced in the appraisal of postoperative wounds and will be provided with standardized criteria and instruction regarding assessment.

Secondary endpoints will include length of hospital stay, cost effectiveness, and the clinical efficacy of the device in relation to the degree of contamination, patient comorbidity, and operative demographics. This information will be recorded contemporaneously on standardized clinical

report forms. Data for this study will then be entered into a REDCap database, which uses a MySQL database via a secure web interface with data checks used during data entry to ensure data quality. REDCap includes a complete suite of features to support HIPAA compliance, including a full audit trail, user-based privileges, and integration with the institutional LDAP server. The MySQL database and the web server will both be housed on secure servers operated by the Cleveland Clinic.

Procedures

Preoperative evaluation will include the prospective assessment and recording of demographic data related to the patient and their co-morbidities. Operative details, including any deviation from allocation, will be recorded immediately after the operation (Appendix 1). The post-operative wound will be assessed daily by the attending staff surgeon. A trained reviewer independent from the surgical team performing the intervention will formally assess the wound on post-operative day seven. If the patient is discharged prior to post-operative day 7, an early outpatient assessment will be scheduled for day 7 ± 1 day as is the standard practice of our department. A second formal wound review will be performed at 30 (+/-7) days, which will involve the patient returning to hospital for a physical review of the wound. At this same visit, patients will also complete a supervised, self-reported post-discharge questionnaire (PDQ) with the study investigator to identify any occurrence of SSI during the intervening period between the two clinical assessments. The questionnaire is based on the validated Health Protection Agency surgical site infection surveillance system⁶, which is based on the original CDC definitions (Appendix 2) and has been used in prior high quality randomized trials of SSIs⁶. To our knowledge, this will represent the first time this questionnaire is used in a trial of Prevena™. On day 7 ± 1 day and 30 \pm 7 days a photograph will be taken of the wound to be evaluated by a blinded assessor of wound healing at a later date and scored on a modified 10-point Likert scale (1 = very poorly healed; 10 = fully healed).

Cost Analysis

The objective of the economic evaluation is to explore the relative cost-effectiveness of Prevena™ NPWT compared to standard care. Cost and resource use data will be collected prospectively for both arms of the trial. Trial co-coordinators will identify hospital utilization items and primary care utilization items will be determined by patient interview at the post-operative 30-day clinic visit. Unit costs will be valued in \$ (2015 value). The cost of the intervention (Prevena™ NPWT) will be obtained from the manufacturer. Inpatient care resource items will be sourced from the Cleveland Clinic Reference Costs data. Total resource costs will be obtained by summation of the individual resource costs for each category of resource item accessed by trial patients. Individual resource costs will be obtained by multiplying the resource use by the corresponding unit costs.

Statistical analysis

We hypothesize that the use of Prevena™ incisional NPWT in adults reduces SSI rates in open, re-operative colorectal surgery. For re-operative colorectal surgery, the Department of Colorectal Surgery at the Cleveland Clinic, Ohio has observed a 19.4% overall SSI rate (unpublished internal audit). Assuming a 2.34 fold reduction in SSI rates based on a prior retrospective study in the setting of Colorectal Surgery¹² (19.4% to 8.3%), 298 patients (149 per control and intervention arm) are required to achieve a power of 80% and a two-sided type I error rate of 0.05 (StudySize v3.0, CreoStat HB, Gothenburg, Sweden). As there is only one primary endpoint (SSI development), adjustments for multiplicity are not required.

Results will be analyzed according to the intention to treat principal. For the primary endpoint,

missing data will be handled by the principal of complete-case analysis, thus, participants with missing data will be excluded from the analysis. Descriptive statistical comparisons between the two study groups will be performed with the use of chi-square tests or Fisher's exact test, as appropriate, for categorical end points and analysis-of-variance techniques or Wilcoxon rank-sum tests, as appropriate, for continuous end points. The log-rank tests will be used to compare the time to first surgical-site infection between the two study groups. Kaplan–Meier survival estimates of the time to first surgical-site infection will also be calculated. Analyses will be performed with SPSS version 20.0 (IBM Corp, Armonk, NY, USA). $P<0.05$ will be considered statistically significant. A formal, interim analysis is planned to take place when a total of one hundred patients have been accrued for both arms all together.

References

1. de Lissovoy G, Fraeman K, Hutchins V, et al: Surgical site infection: incidence and impact on hospital utilization and treatment costs. *Am J Infect Control* 37:387-97, 2009
3. Burke JP, O'Connell PR: Surgical site infection and colorectal surgery: a research priority. *Dis Colon Rectum* 57:e390, 2014

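### Randomising the day before surgery leaves the allocation open to the operating surgeon, lets some patients become ineligible after allocation, and gives true emergencies no route into the trial

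*Combined protocol and SAP*

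**What the plan says.** **Timing.** Under Randomization: "Randomization will be performed when the patient attends the last preoperative visit". The reason offered is convenience: "In our department this visit occurs on the day prior to surgery, facilitating ease of enrolment". Assignment is central, with patients "randomly assigned through a concealed centralized secure web based system in a 1:1 ratio".

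**Who knows and who acts.** Departmental surgeons trained in the device "will enroll and operate on patients included in this trial", and "the attending staff surgeon will perform all closures themselves". The order of events is fascial closure, skin staples, then either gauze and tape or the device, in both arms before the ostomy is matured. No sentence withholds the result of the randomisation until that point.

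**Who is eligible.** Study design and patients defines eligibility by the procedure. It excludes laparoscopic and laparoscopic-assisted operations and patients with an active SSI at the time of surgery. On urgency, patients having procedures such as "enterocutaneous fistula repair in both elective and emergency settings are eligible for enrolment". Appendix 1 records urgency as elective, urgent or emergent.

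**What follows a change of plan.** Under Procedures, operative details "including any deviation from allocation, will be recorded immediately after the operation". Statistical analysis specifies intention to treat, with a complete-case rule for a missing primary endpoint. There is no rule for patients found ineligible, or not given the allocated dressing, after randomisation.

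**The concern.** The two arms are treated identically until the skin is closed, so the allocation is not needed until then. Making it a day earlier has three consequences.

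1. **Performance bias.** A surgeon who knows the arm may, without intending to, vary the steps left open: interrupted or running fascial closure, skin preparation, control of contamination. Intention to treat does not remove a difference created this way.
2. **Change after allocation.** The procedure may alter, the approach may alter, or an active SSI may be found on the day. Such a patient has already been randomised. The patient either stays in the comparison without receiving what was allocated, or leaves it for want of an outcome.
3. **Emergencies.** A patient operated on as a true emergency does not attend a visit the day before. The eligibility text and the randomisation text therefore conflict, and the enrolled population could be narrower than the stated one.

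**Working it through.** **Inputs from the plan (Statistical analysis).** Control risk 19.4%, device risk 8.3%, 149 per arm, two-sided 0.05, power 80%.

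**Reproducing the sample size.** Unpooled normal approximation:

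n = (1.960 + 0.842)² × [0.194×0.806 + 0.083×0.917] / (0.194 − 0.083)² = 7.849 × 0.2325 / 0.01232 = 148.1, so 149 per arm and 298 in total.

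This matches the plan. At 149 per arm, power is 79.5% by the pooled normal approximation and 80.4% by exact enumeration of the uncorrected chi-square test. The stated size includes no allowance for patients lost or untreated after randomisation.

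**Dilution.** Assumption: a fraction d of the device arm never receives the device, carries the control risk, and stays in the intention-to-treat set. The device-arm risk becomes 0.083(1 − d) + 0.194d.

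| d | Device-arm risk | Exact power | Normal approx. |
|---|---|---|---|
| 0 | 8.30% | 80.4% | 79.5% |
| 5% | 8.86% | 75.3% | 74.6% |
| 10% | 9.41% | 69.7% | 69.2% |

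**Loss through the complete-case rule.** Assumption: the same share is lost from both arms, with risks unchanged.

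| Share lost | Patients per arm | Normal approx. | Exact power (whole patients) |
|---|---|---|---|
| 5% | 149 × 0.95 = 141.6 | 77.4% | 78.4% (141) |
| 10% | 149 × 0.90 = 134.1 | 75.2% | 76.1% (134) |

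Power is therefore about 78–75%, a smaller cost than dilution.

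**Performance bias.** Assumption: the device has no effect, control risk is 19.4%, and care other than the device multiplies device-arm risk by r. Exact chi-square rejection at 149 per arm:

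| Relative reduction | Device-arm risk | Two-sided rejection | Of which favours the device |
|---|---|---|---|
| 0 | 19.4% | 5.0% | 2.5% |
| 5% | 18.4% | 5.5% | 4.0% |
| 10% | 17.5% | 7.2% | 6.3% |
| 20% | 15.5% | 14.2% | 14.0% |

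**The emergency conflict** needs no arithmetic. Study design and patients admits emergencies and Appendix 1 has a category for them. The only randomisation route is a preoperative visit, of which the plan says "In our department this visit occurs on the day prior to surgery".

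**The case against.** The plan has real safeguards. The same prevention bundle applies in every case: wound protector, glove changes before closure, separate closing instruments. Saline irrigation, closure by the attending surgeon and skin staples are also common to both arms. Little is left to choice at closure beyond fascial technique, so a 20% relative reduction from differential care has no support in the documents, and at 5% the inflation is slight. These points stand. They limit the concern without removing it.

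Four stronger readings are tempting but not supported:

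- **That the surgeon is told the arm.** No sentence says so. The text shows only that the surgeons enrol and that nothing prevents them from knowing.
- **That foreknowledge steers who is enrolled.** Enrolled patients are the ones assigned, through a concealed central system, so enrolment precedes allocation.
- **That eligibility is settled only in theatre.** A prior anastomosis, hernia, fistula, recent laparotomy and planned open approach can largely be known beforehand. Only some criteria can change.
- **That no non-elective patient can be randomised.** The day-before timing describes departmental routine, and an urgent inpatient with a day's notice may fit. The gap concerns true emergencies.

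The surgeon's knowledge of the arm while following the wound is also not a timing matter: the dressing is visible whenever randomisation occurs.

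**Conclusion.** The point holds as a worthwhile and inexpensive design improvement. It does not show that bias will occur or that the sample size is miscalculated; 298 reproduces.

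Three things rest on the text alone: allocation comes a day before it is needed; nothing shields the operating surgeon from it; and true emergencies are eligible without a randomisation route, so those sections must be reconciled.

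The sizes rest on assumed rates, because the documents give none. The dilution range (75.3–69.7% power at 5–10%) requires the affected device-arm patients to stay in the analysis at control risk. The range of about 78–75% applies if they leave as incomplete cases instead. In practice both routes could operate. The rejection rates of 5.5%, 7.2% and 14.2% show sensitivity to unequal care and are not estimates of it.

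**What to change.** Keep consent before surgery. Perform the existing REDCap randomisation in theatre once the qualifying open procedure is confirmed and the skin is stapled, immediately before the dressing is applied. Stapling should be complete, because randomising once the fascia is closed would still reveal the arm before skin closure. Use the same rule for elective, urgent and emergency cases, and align the eligibility and Randomization text accordingly. This fits the existing requirement that dressings precede ostomy maturation.

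**Cost.** A change of protocol wording, a log-in during each case, and a device on hand in theatre. It gives up some of the ease of enrolment that the plan cites for the day-before visit. The required number stays at 298.

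**What it does not do.** It does not blind postoperative assessment, and it does not prevent early removal of the device.

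**If the timing is kept.** Add a randomisation route for emergencies, a rule for post-randomisation ineligibility applied blind to arm, and an allowance in the sample size. For 5–10% lost as incomplete cases the total becomes 298/0.95 = 314 to 298/0.90 = 332. For 5–10% dilution, the pooled formula gives 342 to 386, against 302 with none.

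### No one who calls the primary endpoint is stated to be masked, and the plan does not say whose call stands when assessors disagree

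*Combined protocol and SAP*

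**What the plan says.** Efficacy outcomes defines the primary endpoint as superficial SSI within 30 days, diagnosed by CDC criteria. It adds a safeguard: "All wound assessors will be experienced in the appraisal of postoperative wounds and will be provided with standardized criteria and instruction regarding assessment".

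The plan describes four possible sources of an SSI call.

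- **Attending surgeon.** Procedures: "The post-operative wound will be assessed daily by the attending staff surgeon". Under Randomization, "the attending staff surgeon will perform all closures themselves".
- **Day-7 reviewer.** Procedures: "A trained reviewer independent from the surgical team performing the intervention will formally assess the wound on post-operative day seven".
- **Day-30 reviewer.** Procedures: "A second formal wound review will be performed at 30 (+/-7) days". The person is not named or described.
- **Questionnaire.** The patient completes it with the study investigator at the day-30 visit. The form in Appendix 2 has the trial investigator mark whether the reported SSI meets the definition.

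Blinding is mentioned once, in Procedures, for the assessor who later scores healing from 1 to 10 on the day-7 and day-30 photographs.

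On what can be seen and when, Randomization says of controls "The non-NPWT dressing will be left in place for 48 hours before changing", and of the device arm "The Prevena™ system will remain in place for 7 ± 1 days", with earlier removal possible: "if concern exists for the patients wound, it will be removed, the wound assessed".

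**The concern.** Redness, swelling, pain and discharge all require judgement, and an assessor who knows the arm can lean either way in a borderline case. Standard criteria and training make assessors more alike; they do not remove knowledge of the arm. Independence from the surgical team removes a personal stake in the operation, but it is not masking. The plan already has one blinded assessor and does not use that person for the endpoint that decides the trial.

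If the surgeon records an SSI and a formal reviewer does not, or the reverse, nothing says which entry becomes the endpoint. That leaves the choice to be made later, possibly by someone who knows the arm.

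A secondary point concerns timing. The inpatient review is fixed on day 7, while the device may stay on until day 8. The review can therefore fall before the wound is uncovered, and the order of removal and review is not stated.

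**Working it through.** **Who knows the arm**

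| Source of call | Stated independence | Stated masking |
|---|---|---|
| Attending surgeon, daily | None; closes the wound | None; knows the arm |
| Day-7 reviewer | Independent of the surgical team | None |
| Day-30 reviewer | Not stated | None |
| Investigator, questionnaire | Not stated | None |
| Photograph assessor | Not stated | Blinded, but scores healing, not SSI |

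**The plan's own figure.** Inputs from Statistical analysis: 19.4% versus 8.3%, two-sided 0.05, power 80%. With unpooled variance, n per arm = (1.960 + 0.842)² × (0.194 × 0.806 + 0.083 × 0.917) / 0.111² = 148.1, so 149 per arm and 298 in total. This matches the plan; the sample size is not in question. Exact power of the uncorrected chi-square test at 149 per arm is 80.4%.

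**Sensitivity of the test to differential calling.** Assumptions: 149 per arm, a true rate of 19.4% in both arms (the audit's overall SSI rate, used because no superficial rate is given), uncorrected chi-square, exact binomial enumeration. If a share s of uninfected patients is wrongly called SSI, the observed rate is 0.194 + 0.806 × s. That is 0.2101 for s = 2% and 0.2262 for s = 4%. The expected extra calls are 149 × 0.806 × s, or 2.4 and 4.8 patients.

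| Over-called, controls | Over-called, device | False significant benefit |
|---|---|---|
| 0% | 0% | 2.5% |
| 2% | 0% | 5.3% |
| 4% | 0% | 10.1% |
| 4% | 2% | 5.2% |
| 2% | 2% | 2.5% |
| 4% | 4% | 2.5% |

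At an assumed superficial rate of 12%, the second and third rows become 6.5% and 13.8%.

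**Opposite direction.** With over-calling in the device arm only, at 19.4%, false harm is 5.3% (2%) or 10.1% (4%), and false benefit falls to 1.1% or 0.4%. At the planned effect, the device rate becomes 0.083 + 0.917 × s, that is 0.1013 or 0.1197, and power falls from 80% to 62% or 42%. With equal over-calling in both arms it falls only to 74% or 69%.

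**The case against.** The plan is more structured than it may first appear. The two formal reviews and the questionnaire, which covers the interval between them, largely complement one another. Statistical analysis refers to time to first SSI, and Appendix 1 records SSI type and day. Together these point to any first qualifying SSI counting. A reader might infer that the endpoint has no definition; the documents do not support that. What is missing is a written rule and a way to settle disagreement.

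The surgeon's daily look is not called formal, and the day-30 reviewer may well be the same kind of independent person as on day 7. Both readings are natural, but neither is stated.

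A reader might also infer that covering the wound for about a week hides infections and so favours the device. For the yes/no endpoint, such an infection would have to arise under cover, raise no concern, and be missed at day 7, at day 30 and by the questionnaire. Nothing in the documents shows that this happens often, and Appendix 1 records early removal with its reason. The unequal view is a fact of the design; a bias from it is speculation.

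Finally, the larger figures above assume error in one arm only. That objection stands: the result depends on the difference between arms, and equal error leaves false benefit unchanged.

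**Conclusion.** The gap is real and modest. No assessor of the primary endpoint is stated to be masked, one of them certainly knows the arm, one is unidentified, and no text settles discordant calls. The existing safeguards (CDC criteria, trained assessors, an independent day-7 reviewer) reduce the risk but do not address knowledge of the arm.

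The size cannot be derived from the documents. Under the assumed shares, two or three extra calls in one arm roughly double the chance of a false significant benefit (2.5% to 5.3%), and about five raise it to 10.1%. Partly offsetting error gives 5.2%, and equal error gives 2.5%. The direction is also unknown. A reader should not take these figures as the trial's actual error rate, nor conclude that a positive result would be false. They show that a handful of differential judgements matters at this sample size.

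Separately, the day-7 inpatient review and the 7 ± 1 day device window must be reconciled.

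**What to change.** 1. State that the independent reviewer planned for day 7 also does the day-30 review and the questionnaire classification, is not told the arm, and sees the wound after existing staff have uncovered it. Reconcile the timing of the day-7 review with the device window, leaving the device schedule unchanged.
2. Write the counting rule: a superficial SSI counts if the documented findings from any source meet the CDC criteria, and the arm-unaware reviewer's determination prevails if sources disagree.
3. Add two sensitivity analyses of the primary endpoint: one using only the formal day-7 and day-30 calls, and one using an SSI yes/no reading by the existing blinded assessor from the day-7 and day-30 photographs. Direct examination stays primary, since a photograph cannot convey findings such as tenderness.

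The cost is some scheduling effort and a little extra reading by the photograph assessor; no visits are added. There are limits: skin marks or the patient may reveal the arm, and infections that resolved unseen under the device are not recovered.

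### The final SSI review may take place on day 23, so a discharged patient can have 1 to 7 days of the 30-day primary endpoint with no planned SSI assessment

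*Combined protocol and SAP*

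**What the plan says.** Efficacy outcomes defines the primary endpoint as "the occurrence of superficial surgical site infection within 30 days after the operation".

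Procedures describes how SSI is ascertained:
- The attending surgeon follows the wound: "The post-operative wound will be assessed daily by the attending staff surgeon". No setting or end date is given.
- An independent reviewer assesses the wound on day 7, as an outpatient visit (day 7 ± 1) if the patient has already been discharged.
- "A second formal wound review will be performed at 30 (+/-7) days", for which the patient returns to hospital.
- The questionnaire is completed at that second visit. Its purpose is "to identify any occurrence of SSI during the intervening period between the two clinical assessments".
- A wound photograph is taken in the same two windows and is scored for healing, not for SSI.

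Two other routes could bring an SSI to light. Cost Analysis says "Trial co-coordinators will identify hospital utilization items", with no stated end date, while "primary care utilization items will be determined by patient interview at the post-operative 30-day clinic visit". Appendix 1 records the type of SSI, its day of onset and any procedures for it, with no cut-off day.

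Statistical analysis handles missing primary-endpoint data by complete cases: "participants with missing data will be excluded from the analysis". It assigns chi-square or Fisher's exact tests to categorical endpoints, and plans log-rank and Kaplan–Meier analyses of time to first SSI. It gives no censoring rule, and it does not say whether a review before day 30 counts as complete 30-day data.

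**The concern.** The endpoint runs to day 30, but the last planned look at the wound may come a week earlier. The questionnaire cannot fill the gap, because it is completed at the visit and asks about the time before it. The daily surgeon assessment cannot reasonably be read as continuing after discharge, since the same section brings discharged patients back for outpatient reviews.

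A patient reviewed without SSI on day 23 has a recorded outcome, so the complete-case rule would probably not treat that patient as missing. The patient would then enter the comparison of proportions as event-free at 30 days on the strength of 23 days of planned assessment. Patients seen on day 30 or later are assessed for the whole period. At stake are a few uncounted late infections, a slightly low 30-day rate in both arms, and a small loss of power.

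**Working it through.** **1. The gap (documents only).** The window is 30 − 7 = 23 to 30 + 7 = 37. Days of the endpoint after the final visit = max(0, 30 − visit day):

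| Final visit day | 23 | 24 | 25 | 26 | 27 | 28 | 29 | 30–37 |
|---|---|---|---|---|---|---|---|---|
| Days with no planned SSI assessment | 7 | 6 | 5 | 4 | 3 | 2 | 1 | 0 |

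**2. The plan's sample size.** Inputs from Statistical analysis: 19.4% v 8.3%, two-sided 0.05, 80% power. With unpooled variance, n = (1.960 + 0.842)² × (0.194 × 0.806 + 0.083 × 0.917) / 0.111² = 148.1, so 149 per arm and 298 in total. The plan's figure reproduces. At 149 per arm, the uncorrected two-sided chi-square test has exact power of 80.4% (normal approximation 79.5%). Expected events: 149 × 0.194 + 149 × 0.083 = 28.9 + 12.4 = 41.3.

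**3. Assumptions, none of them in the documents.**
- Between 5% and 15% of 30-day SSIs start on days 24 to 30.
- Visit days are either uniform over days 23 to 37, or triangular with a peak at day 30.
- Onset within days 24 to 30 is either uniform or falls by 20% per day.
- Other routes capture either none or half of the late SSIs that planned assessment misses.
- The planning rates reflect complete 30-day ascertainment of superficial SSI.

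**4. Share of late SSIs that start after the final visit.**
- Uniform visits, uniform onset: mean uncovered days (7 + 6 + 5 + 4 + 3 + 2 + 1)/15 = 1.867, and 1.867/7 = 0.267.
- Triangular visits (weights 1 to 7 on days 23 to 29, total weight 64), uniform onset: 84/64 = 1.3125, and 1.3125/7 = 0.1875.
- Falling onset: 0.209 (uniform visits) and 0.129 (triangular visits).

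**5. Events missed and power.** Both rates are multiplied by 1 − (share in step 4 × late share × (1 − capture)). Missed events are 41.3 × that product. For example, the worst case is 41.3 × 0.267 × 0.15 = 1.65.

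| Onset | Other capture | Events missed | Exact power |
|---|---|---|---|
| Uniform | None | 0.39 to 1.65 | 80.0% to 78.6% |
| Falling | None | 0.27 to 1.30 | 80.1% to 79.0% |
| Uniform | Half | 0.19 to 0.83 | 80.2% to 79.5% |
| Falling | Half | 0.13 to 0.65 | 80.3% to 79.7% |

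In each row the first figure is for triangular visits with a 5% late share, and the second is for uniform visits with a 15% late share. Across all rows the loss is 0.1 to 1.8 points.

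**6. Between-arm effect.** Losing the same fraction k in both arms gives 0.194(1 − k) / 0.083(1 − k) = 0.194/0.083, so the risk ratio is unchanged.

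**The case against.** The strongest objection is materiality. The upper end of the table needs a 15% late share, uniform visit days and no other capture, all at once. Cost Analysis calls this the 30-day visit, so visits probably cluster near day 30. Even the worst case, 1.8 points, is of the same order as the 0.9-point difference between exact and normal-approximation power. The planning rate itself is uncertain: the department "has observed a 19.4% overall SSI rate (unpublished internal audit"), and the audit's follow-up is not described. If the audit missed late SSIs in the same way, nothing is lost against the plan. All of this stands, and it limits the point to an inexpensive improvement.

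It is also fair that the documents are silent on later contact and do not exclude it. Hospital-utilization tracking and the Appendix 1 fields could bring in late events. Neither is a scheduled wound assessment, however, and primary care use is asked about only at the visit, so these routes narrow the gap without closing it.

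A reader might infer three stronger things:
- *That late SSIs will go unrecorded.* The text supports only that no assessment after the visit is described.
- *That the comparison is biased.* Nothing in the documents suggests that visit timing or late onset differs by arm.
- *That power falls well below 80%.* Missing 5%, 10% or 15% of all SSIs would give 77.1%, 74.5% or 71.7% (normal approximation, from 79.5%). Here at most 0.267 × 15% = 4% of SSIs are missed.

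**Conclusion.** The mismatch between endpoint and ascertainment is real and follows from the text. A discharged patient whose final review is clean on days 23 to 29 has 1 to 7 endpoint days without a planned SSI assessment. That this patient would count as no SSI in the comparison of proportions is an inference, because the plan gives no rule. The onset-day field lets events after day 30 be set aside for late visits, but it does not help with early ones. Log-rank and Kaplan–Meier methods can handle unequal follow-up, but only with a censoring rule, and none is stated.

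The effect is small: about 0.1 to 1.7 of 41 expected events and at most about 2 points of power, with no between-arm bias expected. Confidence is high for the window arithmetic. The event and power figures are illustrations that rest on the assumptions listed above. This is an optional improvement and does not threaten the trial's validity.

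**What to change.** **Scheduling.** Keep 30 ± 7 days as the accepted window, but book the final review and questionnaire for day 30 to 37 where possible. This needs no extra visit or form. The cost is slightly longer questionnaire recall.

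**Telephone contact for the remainder.** For patients seen before day 30 without SSI, repeat the Appendix 2 items by telephone at or just after day 30 and score them in the existing investigator box. If rebooking leaves 10% to 20% seen early (an assumption), this is (298 − 41.3) × 0.10 to 0.20 = about 26 to 51 calls. Someone must make them, and day-30 status for these patients would be self-reported. Calls without rebooking are poor value: 7/15 = 46.7% (uniform) or 28/64 = 43.75% (triangular) of visits fall before day 30, so about 112 to 120 calls would recover 0.1 to 1.7 events.

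**SAP wording.** Censor log-rank and Kaplan–Meier follow-up at the earlier of last contact and day 30. State separately how patients last contacted before day 30 are classified in the comparison of proportions, because censoring does not settle that.

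**Not advised: a strict day 30 to 37 window.** It shortens the window from 15 days to 8, and patients who miss it would be excluded as missing. With no events lost, exact power is 80.3% at 147 per arm and 78.4% at 141, so about 2 to 8 extra missing patients per arm would cancel the gain.
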